- If CXCL9 is measured below threshold, patients will continue the extended monitoring period until Day 98 \pm 3 days or until a second HSCT is planned.

Criteria not to start treatment during monitoring or extended monitoring

Patients presenting the following conditions at time of initiation of emapalumab treatment will not be eligible to receive emapalumab and will move to the phone-call follow-up period for non-emapalumab treated patients (see section 3.4.5).

- Uncontrolled infections (defined as clinically active infection regardless of treatment).
- Clinical manifestations of infections representing exclusion criteria (i.e. Atypical mycobacteria, Salmonella, Histoplasma capsulatum, Herpes zoster).
- Re-occurrence or progression of the underlying malignant disease based on medical judgment.
- GvHD.

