4.1 Inclusion criteria

1. Informed consent form signed by the patient (as required by law) or by the patient's legally authorized representative(s) with the assent of patients who are legally capable of providing it, as applicable.
2. Recipients of allogeneic HSCT and at high risk of GF, based on at least one of the following criteria:
 - Receiving reduced intensity conditioning (RIC) or non-myeloablative (NMA) conditioning, combined with a non-malignant disease or with a graft from Bone Marrow (BM).
 - *Ex vivo* T cell depleted graft.
 - Graft from mismatched unrelated or haploidentical donor.
 - Graft from Umbilical Cord Blood (UCB).
3. Patients requiring allo-HSCT with the following underlying diseases:
 - Malignant disease with high risk of GF, i.e. Acute Myeloid Leukemia (AML) and Acute Lymphoblastic Leukemia (ALL), with primary induction failure, second partial remission or relapse; Chronic Myeloid Leukemia (CML) in blastic phase (circulating blast or blast above 5% in biopsy); Non Hodgkin and Hodgkin Lymphoma and multiple myeloma with primary induction failure, second partial remission or relapse; myelodysplastic syndromes (MDS) and myeloproliferative disorders (MPD) with splenomegaly; myelofibrosis with portal hypertension pre-transplant; MDS/MPD overlap syndromes.
 - Non-malignant hematological diseases (e.g. autoimmune and metabolic disorders, aplastic anemia, Sickle cell anemia, Fanconi anemia, Diamond-Blackfan anemia, thalassemia, osteopetrosis, Wiskott-Aldrich syndrome, severe combined immunodeficiency, Hemophagocytic lymphohistiocytosis and other immunoregulatory disorders).
4. Male and female patients.
5. Children aged at least 1 year and adults. Once the appropriate dose has been determined in one of the three cohorts and safety has been assessed by the IDMC, children less than 1 year old may be included in the study.
6. Females of child-bearing potential, defined as all women physiologically capable of becoming pregnant, require the use of highly effective contraceptive measures from screening until 6 months after the last study drug administration.

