7.2 Safety

- Occurrence of relapse, defined as cumulative incidence of reoccurring malignant underlying disease from HSCT up to EoS visit.
- Occurrence of AEs up to EoS visit.
- Occurrence of AEs leading to discontinuation of study treatment.
- Change from baseline in vital signs, laboratory parameters up to EoS visit.

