8.3.4 Post-HSCT clinical assessments

Several clinical assessments are performed post-HSCT during monitoring, treatment and follow up. These assessments are reported in the assessment schedule under clinical assessments from Table 5a to Table 7b.

- Monitoring of occurrence of GvHD and/or engraftment syndrome, graft failure and graft rejection will be assessed during the monitoring, extended monitoring, treatment and follow-up period. Information on the severity and clinical characteristics of GvHD, engraftment syndrome, graft failure and graft rejection (in case of occurrence) will be collected in the eCRF.
- Re-occurrence or progression of the underlying malignant diseases will be monitored prior to treatment initiation, during treatment and follow-up period as indicated in the assessment schedule. Re-occurrence or progression of the disease will be assessed by measuring the minimal residual disease (MRD) in patients with malignant underlying disease.

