11.1.2 Emapalumab permanent discontinuation

Study drug must be permanently discontinued in the following situations:

- Any treatment emergent adverse reaction (i.e. assessed as related), which is considered as life-threatening.
- Any medical condition that the Investigator or Sponsor determines may jeopardize the subject's safety.
- Re-occurrence of malignant disease as judged by the investigator based on clinical assessment including MRD monitoring.

In the situations described above, IDMC will be promptly informed and involved in evaluation of the patient's data.

Other situations that must lead to treatment permanent discontinuation are:

- Pregnancy.
- If a re-transplant is needed based on medical judgment.
- Graft failure.

The reason for study treatment discontinuation should be documented as appropriate in the eCRF.

The Investigator can decide at any time during the study to discontinue the treatment in a patient based on medical judgment, taking into account the benefit/risk ratio for continuing the treatment.

Decision to discontinue treatment will have no impact on the patient's care. All patients who discontinue treatment will be treated according to local medical practice. A subject who prematurely discontinues study treatment is NOT considered as withdrawn from the study. All assessments relevant to EoT visit must be performed and the patient will enter the follow-up period.

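### The relapse endpoint in section 7.2 counts only reoccurring disease, so progression of a malignancy that never cleared after HSCT is monitored but not counted in it

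*Combined protocol and SAP*

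**What the plan says.** Criterion 3 in section 4.1 sets out which malignancies qualify. For acute leukaemia it reads "Acute Myeloid Leukemia (AML) and Acute Lymphoblastic Leukemia (ALL), with primary induction failure, second partial remission or relapse". For lymphoma and myeloma it reads "Non Hodgkin and Hodgkin Lymphoma and multiple myeloma with primary induction failure, second partial remission or relapse". CML qualifies as "Chronic Myeloid Leukemia (CML) in blastic phase". MDS, myeloproliferative disorders and myelofibrosis qualify on other features, such as an enlarged spleen or portal hypertension. No criterion asks for complete remission before HSCT.

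Relapse is the first safety endpoint in section 7.2: "Occurrence of relapse, defined as cumulative incidence of reoccurring malignant underlying disease from HSCT up to EoS visit". In section 11.1.2 the malignancy-specific reason for permanent discontinuation is "Re-occurrence of malignant disease as judged by the investigator based on clinical assessment including MRD monitoring".

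Other places use a wider term. Among the conditions that bar the start of treatment, section 3.4.3 lists "Re-occurrence or progression of the underlying malignant disease based on medical judgment". Section 8.3.4 says "Re-occurrence or progression of the disease will be assessed by measuring the minimal residual disease (MRD) in patients with malignant underlying disease". The MRD footnote to Tables 6a and 6b and the MRD row of Tables 7a and 7b also name progression. Section 3.4.5, Tables 2 and 3, and section 10.2.5.2 go back to the narrower term.

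Sections 10.2 and 10.2.4 name possible weakening of graft-versus-tumour activity as a risk, and 10.2.4 calls the effects in malignancy unknown.

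**The concern.** In ordinary language, disease has to go away before it can re-occur. A patient who is transplanted with disease present, never clears it and then worsens has not relapsed in that sense. Criterion 3 admits many such patients, and worsening of uncleared disease is one direct way that a loss of graft-versus-tumour effect would show.

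So the plan measures progression (8.3.4, Tables 6 and 7) and treats it as a reason not to give a first dose (3.4.3), yet leaves it out of the one safety endpoint aimed at this risk. Nor is it named in the malignancy bullet of 11.1.2. The endpoint could then look reassuring in the patients for whom the question matters most.

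**Working it through.** There is no stated figure to reproduce, because the point concerns a definition. The check is a comparison of texts followed by a formula for the size of the gap.

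**Where progression is named**

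| Place | Purpose | Re-occurrence | Progression |
|---|---|---|---|
| 3.4.3 | bar to starting treatment | yes | yes |
| 8.3.4 | what MRD testing assesses | yes | yes |
| Tables 6a/6b, MRD footnote | reason for MRD | yes | yes |
| Tables 7a/7b, MRD row | follow-up record | yes | yes |
| 3.4.5; Tables 2 and 3 | route to follow-up if untreated | yes | no |
| 10.2.5.2 | risk minimisation | yes | no |
| 11.1.2 | permanent discontinuation | yes | no |
| 7.2 | relapse endpoint | yes | no |

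**Reference state.** Tables 5a and 5b have no MRD row at screening, Day 0 or during monitoring. For treated patients the first scheduled MRD is at dose 1. The baseline characteristics in section 8.1 cover diagnosis, date of onset and ECOG status, but not remission status at HSCT. A positive MRD at dose 1 can therefore be read as disease carried through the transplant or as disease that has returned. Under the 7.2 wording the first is not counted and the second is.

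**Size of the gap.** Let q be the share of malignant patients whose disease never clears and progresses, and r the relapse rate among the remaining malignant patients.

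- Counted by 7.2 as written: (1 − q) × r
- Counted if progression is included: (1 − q) × r + q
- Difference: q

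The documents give neither q nor r, so the values below are assumptions.

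| q | r | 7.2 as written | with progression |
|---|---|---|---|
| 0.1 | 0.2 | 0.9 × 0.2 = 18% | 28% |
| 0.4 | 0.2 | 0.6 × 0.2 = 12% | 52% |
| 0.1 | 0.4 | 0.9 × 0.4 = 36% | 46% |
| 0.4 | 0.4 | 0.6 × 0.4 = 24% | 64% |

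If q is 0, nothing is missed. With r held fixed, the endpoint as written falls as q rises, because fewer patients are left who could relapse. It can therefore improve while disease control gets worse.

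**The case against.** The strongest reply is that the reading is too literal. The protocol defines neither re-occurrence nor relapse, and section 3.4.5 restates the bar in 3.4.3 without the word progression, so the short form may be the drafter's shorthand. Section 12.5 leaves full statistical detail to the SAP. The text available for this review has no separate SAP definition of the event, so a fuller one cannot be ruled out. All analyses are exploratory, and no interim or stopping rule uses a relapse rate. This lowers the stakes but does not remove the ambiguity: two analysts working from 7.2 and 8.3.4 could count different patients.

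Four stronger readings are tempting, and the documents do not support them.

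- **Progression goes unseen.** It does not. MRD results are recorded, section 9.1.1 makes worsening of a pre-existing disease an adverse event, AEs are collected to EoS, and survival is followed for 3 years.
- **A patient with persistent or progressing disease must stay on drug.** Section 11.1.2 also has a general safety clause and lets the investigator stop at any time. Its malignancy bullet rests on clinical judgement, not on an MRD value alone.
- **The wording changes who is evaluable.** Section 11.1.4 keeps patients evaluable when withdrawal is for safety, and relapse is listed as a safety endpoint. Stopping for re-occurrence, stopping under the general clause, or continuing would most naturally all leave the patient evaluable.
- **The 40% quota applied to 250 gives a minimum number affected.** The 250 is an approximate maximum of monitored patients, and section 12.1 expects only 10 to 30% to meet the primary graft failure trigger. The quota is set at screening, not among treated patients.

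**Conclusion.** The point holds as a mismatch between what is monitored and what is counted. As written, 7.2 leaves progression of uncleared disease out of the only safety endpoint specific to the graft-versus-tumour risk, so that endpoint can understate the risk. The understatement equals q, for which the documents give no value.

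This rests on two assumptions: that reoccurring carries its ordinary meaning, and that no fuller definition exists elsewhere. It also rests on many malignant patients having disease at HSCT. Criterion 3 supports that for failed induction, partial remission and CML in blast phase. It is less certain for relapse, which could mean a past relapse, and for MDS, myeloproliferative disorders and myelofibrosis, which are not defined by remission state. Patients who clear disease after HSCT and later relapse are counted correctly.

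A reader might go further and infer that persistence should itself be an event. The documents do not support that. Section 8.3.4 and Tables 7a/7b name progression, not persistence. Dose 1 can fall as early as Day 1, so counting persistence would score disease that was present before any drug exposure as a safety event and blur the signal.

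**What to change.** - In 7.2, define the event as re-occurrence or progression of the underlying malignancy after HSCT, in line with 8.3.4 and Tables 7a/7b. Carry the same definition into the SAP.
- Record disease or remission status at HSCT in the eCRF, taken from the records already needed to verify criterion 3, and report the endpoint by that status.
- Show persistence without progression as a separate descriptive category, not as an event.
- Reconcile the wording of 3.4.3, 3.4.5, 8.3.4 and 11.1.2. Which discontinuation rule applies is for the sponsor to decide.

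The cost is a change of wording and one or two eCRF fields, with no new procedure. The reported event rate will be somewhat higher.

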7.3 Immunogenicity

- Occurrence of antibodies against emapalumab (ADA) and Nab from start of treatment up to EoS visit.

7.4 Pharmacokinetic

- Serum concentrations of free emapalumab.
- PK parameters by non-compartmental analysis (NCA): C_{max} (peak serum concentration), C_{trough} (concentration just before administration), C_{meantau} (mean concentration over a dosing interval), AUC_{tau} (area under curve of a dosing interval), and other parameters as applicable.
- Population PK parameters, as applicable.

7.5 Pharmacodynamics

- Serum concentrations of free IFN γ (before emapalumab treatment), total IFN γ (free + bound to emapalumab), CXCL9 (as marker of IFN γ neutralization).
- Exploratory inflammatory biomarkers relevant to emapalumab mechanism, condition, underlying disease (e.g. soluble interleukin 2 receptor alpha [sIL2R α], ferritin, interleukin-6 [IL-6], tumor necrosis factor alpha [TNF α] and soluble CD163 [sCD163]).
- Exploratory blood tests measuring cell subsets (e.g. fluorescence-activated cell sorting [FACS] for analysis of specific T cell and/or macrophage subsets).

7.6 Exploratory endpoints

- CXCL9 and other biomarkers relevant to the diagnostic test development measured with different analytical technologies.

8 VISIT SCHEDULE AND STUDY ASSESSMENTS

The visit schedule and the study assessments for patients of **weight ≥ 30 kg** are described in Table 5a (Screening, HSCT, monitoring and extended monitoring periods), Table 6a (Treatment period), Table 7a (Follow-up period, unscheduled visit and withdrawal visit).

The visit schedule and the study assessments for patients of **weight < 30 kg** are described in Table 5b (Screening, HSCT, monitoring and extended monitoring periods), Table 6b (Treatment period), Table 7b (Follow-up period, unscheduled visit and withdrawal visit). Some assessments are not performed in patients of **weight < 15 kg** and these are indicated with an (*) in the assessment schedule.

Visits must occur on the designated day with allowed window as indicated. The same assessment schedule is foreseen for Cohort 1, 2 and 3.

The assessments that are mandatory during a visit are marked with an X. Optional assessment to be performed based on medical judgment are marked with an (X).

Table 5a: Schedule of assessments for Screening, HSCT, monitoring and extended monitoring (cohort 1, 2 and 3) – Patients ≥ 30 kg

PERIOD (Duration)	SCREENING (Up to 13 days)	HSCT ¹ (1 day)	MONITORING (Up to 42 ±1 days)	EXTENDED MONITORING (Up to 98 ±3 days)	
VISITS Days ± visit window	SD -21 to SD-8	D0	MD1, MD2, MD3, MD4, MD5, MD6, MD7 MD9, MD11, MD13, MD15, MD17, MD19, MD21, MD24±1, MD27±1, MD30±1, MD33±1, MD36±1, MD39±1, MD42 ±1	Visits every 7±1 days First EM visit is 7±1 days from the last day in the monitoring period (patient transition to EM period as soon as ANC ≥500 in the monitoring)	
Demographics and baseline characteristics	Informed Consent	X			
	Demographics	X			
	Relevant medical history and previous treatments	X			
	Donor and graft characteristics		X		
Clinical Assessments	Stratification by underlying disease (malignant/non-malignant)	X			
	Review of inclusion/exclusion criteria ²	X	X		
	Assess eligibility to emapalumab treatment			X	
	Height	X			
	Weight	X	X		
	Vital Signs (BP, HR, body temperature)	X	X	X	
	Chest X-Ray	X		Anytime a pulmonary infection is suspected	
	12-Lead ECG	X			
	Physical Examination	X	X	As clinically indicated	
Occurrence of GvHD and/or engraftment syndrome, graft failure, graft rejection			X		
Laboratory procedures	Search for infections ³		X ³	Anytime an infection is suspected	
	TB testing ²	X		Anytime an infection is suspected	
	Serum pregnancy test	X			
	Urine pregnancy test		X	MD30	Every 4 weeks (from last pregnancy test)
	Urinalysis	X			
	Coagulation	X			
	Biochemistry ⁴	X			
	Hematology including differential hematology ⁴	X			X
	Absolute Neutrophil Count (ANC)		X ⁵	X	
	Donor chimerism ⁶			MD1, MD7, MD15, MD21, MD27, MD33, MD39	X
	HLA antibodies against donor cells		X		
CXCL9 ⁸		X ⁵	X		
Inflammatory biomarkers ⁷	X	X	X		
AEs & Concomitant medications	X	X	X		

Table 5a foot notes
Abbreviations: SD: Screening Day; MD: Monitoring Day; D: Day; EM: Extended Monitoring; BP: Blood Pressure; HR: Heart Rate; TB: Tuberculosis; ANC: Absolute Neutrophil Count; HLA: Human Leukocyte Antigen; CXCL9: C-X-C Motif Chemokine Ligand 9; AEs: Adverse Events
1: All assessments/procedures must be performed pre HSCT, unless otherwise specified
2: TB results from the screening (IFN γ -release assay/PPD test) must be available at the latest prior to HSCT for eligibility assessment.
3: Atypical mycobacteria, salmonella, histoplasma capsulatum, herpes zoster, HHV6, CMV, EBV, adenovirus, parvovirus.
4: Biochemistry: Glucose, C-reactive protein (CRP), Sodium, Potassium, Chloride, Calcium, Magnesium and Phosphate, AST, ALT, γ GT, ALP, LDH, bilirubin (total, direct and indirect), triglycerides, cholesterol (total and HDL), Albumin, creatinine, urea (fast conditions whenever possible), Ferritin. Hematology: hematocrit, hemoglobin, platelets, RBC, WBC. Hematology differential: lymphocytes, monocytes, neutrophils.
5: Pre HSCT
6: Donor chimerism must be assessed at the monitoring visits as indicated unless the patient transitioned to extended monitoring period or treatment
7: Free IFN γ , CXCL9 and other inflammatory biomarkers in serum (e.g. IL-6, TNF α , sCD163 and sIL2R α). These samples may also be used to assess baseline values of ADA.
8: The CXCL9 sample is analysed locally with a device provided by the Sponsor.

Table 5b: Schedule of assessments for Screening, HSCT, monitoring and extended monitoring (cohort 1, 2 and 3) – Patient weight < 30 kg

PERIOD (Duration)	SCREENING (Up to 13 days)	HSCT ¹ (1 day)	MONITORING (Up to 42 ±1 days)	EXTENDED MONITORING (Up to 98 ±3 days)	
VISITS Days ± visit window	SD -21 to SD-8	D0	MD1, MD2, MD3, MD4, MD5, MD6, MD7 MD9, MD11, MD13, MD15, MD17, MD19, MD21, MD24±1, MD27±1, MD30±1, MD33±1, MD36±1, MD39±1, MD42 ±1	Visits every 7±1 days First EM visit is 7±1 days from the last day in the monitoring period (patient transition to EM period as soon as ANC ≥500 in the monitoring)	
Demographics and baseline characteristics	Informed Consent	X			
	Demographics	X			
	Relevant medical history and previous treatments	X			
	Donor and graft characteristics		X		
Clinical Assessments	Stratification by underlying disease (malignant/non-malignant)	X			
	Review of inclusion/exclusion criteria ²	X	X		
	Assess eligibility to emapalumab treatment			X	
	Height	X			
	Weight	X	X		
	Vital Signs (BP, HR, body temperature)	X	X	X	
	Chest X-Ray	X	Anytime a pulmonary infection is suspected		
	12-Lead ECG	X			
	Physical Examination	X	X	As clinically indicated	
Occurrence of GvHD and/or engraftment syndrome, graft failure, graft rejection			X		
Laboratory procedures	Search for infections ³		X	Anytime an infection is suspected	
	TB testing ²	X		Anytime an infection is suspected	
	Urinalysis	X			
	Coagulation	X			
	Biochemistry ⁴	X			
	Hematology including differential hematology ⁴	X			
	Absolute Neutrophil Count (ANC)		X ⁵	X (except at MD6 for patients below 15 kg)	X
	Donor chimerism			As clinically indicated	
	HLA antibodies against donor cells		X		
	CXCL9 ⁷		X ³	X (except at MD6 for patients below 15 kg)	
Inflammatory biomarkers ⁶	X	X	X (except at MD6 for patients below 15 kg)		
AEs & Concomitant medications	X	X	X		

Table 5b foot notes

Abbreviations: SD: Screening Day; MD: Monitoring Day; D: Day; EM: Extended Monitoring; BP: Blood Pressure; HR: Heart Rate; ECG: Electrocardiogram; GvHD: Graft versus Host Disease; TB: Tuberculosis; ANC: Absolute Neutrophil Count; HLA: Human Leukocyte Antigen; CXCL9: C-X-C Motif Chemokine Ligand 9; AEs: Adverse Events

1: All assessments/procedures must be performed pre HSCT, unless otherwise specified.
2: TB results from the screening (IFN γ -release assay/PPD test) must be available at the latest prior to HSCT for eligibility assessment.
3: Atypical mycobacteria, salmonella, histoplasma capsulatum, herpes zoster, HHV6, CMV, EBV, adenovirus, parvovirus.
4: Biochemistry: Glucose, C-reactive protein (CRP), Sodium, Potassium, Chloride, Calcium, Magnesium and Phosphate, AST, ALT, γ GT, ALP, LDH, bilirubin (total, direct and indirect), triglycerides, cholesterol (total and HDL), Albumin, creatinine, urea (fast conditions whenever possible), Ferritin. Hematology: hematocrit, hemoglobin, platelets, RBC, WBC. Hematology differential: lymphocytes, monocytes, neutrophils.
5: Pre HSCT.
6: Free IFN γ , CXCL9 and other inflammatory biomarkers in serum (e.g. IL-6, TNF α , sCD163 and sIL2R α). These samples may also be used to assess baseline values of ADA.
7: The CXCL9 sample is analysed locally with a device provided by the Sponsor.

Table 6a: Schedule of assessments for Treatment period (Cohort 1, 2 and 3) – Patients weight \geq 30 kg

PERIOD (Duration)	TREATMENT ¹ (Up to 56 days)															EoT	
VISITS	Dose 1	Dose 2	Dose 3	Dose 4	Dose 5	Dose 6	Dose 7	Dose 8	Dose 9	Dose 10	Dose 11	Dose 12	Dose 13	Dose 14	Dose 15	Only for patients that discontinue treatment or engraft before dose 15	
Days \pm visit window	TD 0	TD 3	3 or 4 days from previous dose													3 days from engraftment (if before dose 15) or treatment discontinuation	
Study drug administration	X ²	X	X	X	X	X	X	X	X	X	X	X	X	X	X		
Anti-viral prophylaxis ³	X	X	X	X	X	X	X	X	X	X	X	X	X	X	X	X	
Clinical Assessments	Vital Signs ⁴	X	X	X	X	X	X	X	X	X	X	X	X	X	X	X	
	12-lead ECG	X														X	
	Chest X-Ray	Only in case of clinical suspicion of pulmonary infection														X	
	Physical Examination	X	As medically required														X
	Weight ⁵	X	X	X	X	X	X	X	X	X	X	X	X	X	X	X	X
Laboratory Procedures	Record GvHD, engraftment syndrome, GF, graft rejection	X	X	X	X	X	X	X	X	X	X	X	X	X	X	X	
	Biochemistry and hematology including differential hematology ⁶	X		X		X		X		X		X		X		X	
	ANC		X		X		X		X		X		X		X		
	Coagulation															X	
	MRD ⁷	X										X				X ⁸	
	Urine pregnancy test	X							X							X	
	Urinalysis	X	X	X	X	X	X	X	X	X	X	X	X	X	X	X	X
	Atypical Mycobacteria, Salmonella, Histoplasma, HZ	if an infection is suspected														X	
	HHV6, CMV, EBV, Adenovirus, Parvovirus	X	Repeat at dose 5 and dose 10 (only in patients positive to these infections prior to treatment) at all other visits only if an infection is suspected														X
	TB testing	X ⁹	if an infection is suspected														X
	Cells subsets	X		X ¹¹		X ¹¹		X ¹¹		X ¹¹		X ¹¹		X ¹¹		X ¹¹	X ¹¹
	Donor chimerism					X		X		X		X		X		X	X
	Inflammatory biomarkers ¹⁰	Pre/post	X	X	X	X	X	X	X	X	X	X	X	X	X	X	X
HLA antibodies against donor cells								X								X	
PK	Pre/	Pre/	Pre/	Pre/	Pre/		Pre/		Pre/		Pre/		Pre/		Pre/	X	

PERIOD (Duration)		TREATMENT ¹ (Up to 56 days)														EoT		
VISITS		Dose 1	Dose 2	Dose 3	Dose 4	Dose 5	Dose 6	Dose 7	Dose 8	Dose 9	Dose 10	Dose 11	Dose 12	Dose 13	Dose 14		Dose 15	
Days ± visit window		TD 0	TD 3	3 or 4 days from previous dose												3 days from engraftment (if before dose 15) or treatment discontinuation		
Antibodies against emapalumab		post X	post	post	post	post		post		post		post		post		post	X	X
AEs & Concomitant medications		X																

Table 6a Foot Notes

Abbreviations: TD: Treatment Day; ECG: Electrocardiogram; MRD: Minimal Residual Disease; HZ: Herpes zoster; HHV: Human Herpes Virus; CMV: Cytomegalovirus; EBV: Epstein-Barr Virus; GF: Graft Failure; GvHD: Graft versus Host Disease; PK: pharmacokinetics; AEs: Adverse Events

1: It is recommended that all assessments/procedures are performed pre dose, unless otherwise specified

2: First infusion should be done within 12 hours from CXCL9 sample collection time (levels above threshold)

3: Prophylaxis against HZ virus infection must be in place prior to treatment and must be maintained until approximately 2 emapalumab half lives (i.e. approximately 44 days) after end of treatment

4: Vital signs include body temperature, heart rate, blood pressure. Heart rate/blood pressure must be measured pre-dose, within 30 minutes from start of infusion and at 1 and 2 hours post-infusion. Temperature only pre-dose. More frequent measurements will be done in case is medically indicated.

5: Within 24 hours of the planned infusion

6: Biochemistry: Glucose, C-reactive protein (CRP), Sodium, Potassium, Chloride, Calcium, Magnesium and Phosphate, AST, ALT, γ GT, ALP, LDH, bilirubin (total, direct and indirect), triglycerides, cholesterol (total and HDL), Albumin, creatinine, urea (fasting conditions whenever possible), Ferritin. Hematology: hematocrit, hemoglobin, platelets, RBC, WBC. Hematology differential: lymphocytes, monocytes, neutrophils.

7: MRD is performed in malignant patients only (in order to monitor re-occurrence or progression of the malignant disease).

8: MRD should be done at EoT only if EoT occurs prior to dose 11.

9: TB test prior to treatment must be repeated only if the test performed at screening occurred more than 30 days before treatment or if there is clinical suspicion of TB. Availability of the results of the TB test (if repeated prior to emapalumab administration) is not required provided that (i) results from the test performed at screening are available (ii) the microbiological analysis of the sample collected prior to treatment is ongoing and (iii) the patient clinical condition is not indicative of the presence of an active infection.

10: Free IFN γ (pre-dose only before dose 1) and total IFN γ , CXCL9 and other inflammatory biomarkers in serum (e.g. IL-6, TNF α , sCD163 and sIL2R α).

11: The cell subsets sample will be collected only if the lymphocyte counts from the previous visit are above a certain threshold (defined in the laboratory manual)

Table 6b: Schedule of assessments - Treatment period (Cohort 1, 2 and 3) – Patient weight < 30 kg

PERIOD (Duration)	TREATMENT ¹ (Up to 56 days)															EoT	
VISITS	Dose 1	Dose 2	Dose 3	Dose 4	Dose 5	Dose 6	Dose 7	Dose 8	Dose 9	Dose 10	Dose 11	Dose 12	Dose 13	Dose 14	Dose 15	Only for patients that discontinue treatment or engraft before dose 15	
Days ± visit window	TD 0	TD 3	3 or 4 days from previous dose													3 days from engraftment (if before dose 15) or treatment discontinuation	
Study drug administration	X ²	X	X	X	X	X	X	X	X	X	X	X	X	X	X		
Anti-viral prophylaxis ³	X	X	X	X	X	X	X	X	X	X	X	X	X	X	X	X	
Clinical Assessments	Vital Signs ⁴	X	X	X	X	X	X	X	X	X	X	X	X	X	X	X	
	12-lead ECG	X														X	
	Chest X-Ray	Only in case of clinical suspicion of pulmonary infection														X	
	Physical Examination	X	As medically required														X
	Weight ⁵	X	X	X	X	X	X	X	X	X	X	X	X	X	X	X	X
Laboratory Procedures	Record GvHD, engraftment syndrome, GF, graft rejection	X	X	X	X	X	X	X	X	X	X	X	X	X	X	X	
	Biochemistry and hematology including differential hematology ⁶	X		X		X		X		X		X		X		X	
	ANC		X*		X*		X*		X		X		X		X		
	Coagulation															X	
	MRD ⁷	X*										X*				X ^{8*}	
	Urinalysis	X	X	X	X	X	X	X	X	X	X	X	X	X	X	X	X
	Atypical Mycobacteria, Salmonella, Histoplasma, HZ	if an infection is suspected														X*	
	HHV6, CMV, EBV, Adenovirus, Parvovirus		if an infection is suspected														
	TB testing	X ⁹	if an infection is suspected														X
	Donor chimerism	As clinically indicated															X*
All sampling pre-dose unless otherwise specified	Inflammatory biomarkers ¹⁰	Pre/post	X*	X	X*	X	X*	X	X	X	X	X	X	X	X	X	
	HLA antibodies against donor cells															X	
	PK	Pre/post	Pre/post	Pre/post	Pre/post	Pre/post		Pre/post		Pre/post		Pre/post		Pre/post		Pre/post	

PERIOD (Duration)		TREATMENT ¹ (Up to 56 days)															EoT
VISITS		Dose 1	Dose 2	Dose 3	Dose 4	Dose 5	Dose 6	Dose 7	Dose 8	Dose 9	Dose 10	Dose 11	Dose 12	Dose 13	Dose 14	Dose 15	
Days ± visit window		TD 0	TD 3	3 or 4 days from previous dose													3 days from engraftment (if before dose 15) or treatment discontinuation
	Antibodies against emapalumab	X						X								X	X
AEs & Concomitant medications		X															

Table 6b Foot Notes	
Abbreviations : EoT : End of Treatment ; TD : Treatment Day ; ECG : Electrocardiogram ; MRD : Minimal Residual Disease; HZ: Herpes zoster; HHV: Human Herpes Virus; CMV: Cytomegalovirus; EBV: Epstein-Barr Virus; GF: Graft Failure; GvHD: Graft versus Host Disease; HLA: Human Leukocyte Antigen; PK: pharmacokinetics; AEs: Adverse Events	
*This sample is not collected for patients < 15 kg and will be performed as clinically indicated	
1: It is recommended that all assessments/procedures are performed pre dose, unless otherwise specified	
2: First infusion should be done within 12 hours from CXCL9 sample collection time (levels above threshold)	
3: Prophylaxis against HZ virus infection must be in place prior to treatment and must be maintained until approximately 2 emapalumab half lives (i.e. approximately 44 days) after end of treatment	
4: Vital signs include body temperature, heart rate, blood pressure. Heart rate/blood pressure must be measured pre-dose, within 30 minutes from start of infusion and at 1 and 2 hours post-infusion. Temperature only pre-dose. More frequent measurements will be done in case is medically indicated.	
5: Within 24 hours of the planned infusion	
6: Biochemistry: Glucose, C-reactive protein (CRP), Sodium, Potassium, Chloride, Calcium, Magnesium and Phosphate, AST, ALT, Γ gt, ALP, LDH, bilirubin (total, direct and indirect), triglycerides, cholesterol (total and HDL), Albumin, creatinine, urea (fasting conditions whenever possible), Ferritin. Hematology: hematocrit, hemoglobin, platelets, RBC, WBC. Hematology differential: lymphocytes, monocytes, neutrophils.	
7: MRD is performed in malignant patients only (in order to monitor re-occurrence or progression of the malignant disease).	
8: MRD should be done at EoT only if EoT occurs prior to dose 11.	
9: TB test prior to treatment must be repeated only if the test performed at screening occurred more than 30 days before treatment or if there is clinical suspicion of TB. Availability of the results of the TB test (if repeated prior to emapalumab administration) is not required provided that (i) results from the test performed at screening are available (ii) the microbiological analysis of the sample collected prior to treatment is ongoing and (iii) the patient clinical condition is not indicative of the presence of an active infection.	
10: Free IFN γ (pre-dose only before dose 1) and total IFN γ , CXCL9 and other inflammatory biomarkers in serum (e.g. IL-6, TNF α , Scd163 and Sil2R α).	

Table 7a: Schedule of assessments - Follow-up period, withdrawal visit, EoS and unscheduled visit (Cohort 1, 2 and 3) - Patients weight \geq 30 kg

PERIOD (Duration)	FOLLOW UP ¹ (3 years)											Unscheduled Visit ⁴
	FU 1 ¹	FU 2 ¹	FU 3 ¹	FU 4 ¹	FU 5 ¹	FU6 ¹ or EoS visit ^{1,2} or Withdrawal visit ³	Phone calls					
Days \pm window	Week 1 \pm 2 days	Week 2 \pm 2 days	Week 4 \pm 2 days	Week 8 \pm 1 week	Week 12 \pm 1 week	Week 24 \pm 2 Weeks	6 months \pm 2 weeks from HSCT ²	1 year \pm 4 week from HSCT ^{1,2}	2 year \pm 4 weeks from HSCT ^{1,2}	3 year \pm 4 Weeks from HSCT ^{1,2}		
Clinical Assessments	Vital Signs (BP, HR, body temperature)	X	X	X	X	X	X					X
	12-lead ECG											(X)
	Chest X-ray	Only in case of clinical suspicion of pulmonary infection					X					(X)
	Physical Examination	As medically required					X					X
	Weight	X	X	X	X	X	X					X
	Record engraftment syndrome			X	X	X	X					(X)
Laboratory Procedures	Record GvHD, GF, graft rejection	X	X	X	X	X	X					(X)
	Biochemistry and hematology including differential haematology ⁵	X		X	X	X	X					(X)
	Re-occurrence or progression of underlying malignant disease (MRD)			X	X	X	X					(X)
	Urine Pregnancy Test (if applicable)			X	X	X	X					(X)
	Urinalysis	X	X	X	X	X	X					(X)
	Search for infections ⁶	If an infection is suspected										(X)
	TB testing						X					(X)
	Cells subsets			X		X	X ⁸					(X)
	Donor chimerism			X	X	X	X					(X)
	Inflammatory biomarkers ⁷	X	X	X	X	X	X					(X)
	HLA antibodies against donor cells						X					(X)
	PK			X	X	X	X ⁸					(X)
	Antibodies against emapalumab			X		X	X ⁸					(X)
Survival check and GvHD occurrence recording											X	(X)
Relevant concomitant medications/procedures⁹	X										X	X
AEs	X										Only SAEs related to emapalumab	X

Table 7a Foot Notes
Abbreviations: FU: Follow Up; EoS: End of Study visit; BP: Blood Pressure; HR: Heart Rate; ECG: Electrocardiogram; MRD: Minimal Residual Disease; GF: Graft Failure; GvHD: Graft versus Host Disease; HLA: Human Leukocyte Antigen PK: pharmacokinetics; AEs: Adverse Events
1: This visit is foreseen for emapalumab treated patients. FU week 1 to be scheduled 1 week \pm 2 days from last study drug administration or 1 week after EoT (in case of treatment discontinuation or engraftment before the last dosing 15).
2: This visit is foreseen for non-emapalumab treated patients. The EoS visit for non-emapalumab treated patients must be scheduled within 1 week from the last day in the monitoring periods.
3: In case of premature withdrawal from the study for any reason (except informed consent withdrawal), patients should undergo a withdrawal visit within 1 week from the date of withdrawal.
4: Assessments marked as (X) will be done if considered medically relevant
5: Biochemistry: Glucose, C-reactive protein (CRP), Sodium, Potassium, Chloride, Calcium, Magnesium and Phosphate, AST, ALT, γ GT, ALP, LDH, bilirubin (total, direct and indirect), triglycerides, cholesterol (total and HDL), Albumin, creatinine, urea (fasting conditions whenever possible), Ferritin. Hematology: hematocrit, hemoglobin, platelets, RBC, WBC. Hematology differential: lymphocytes, monocytes, neutrophils.
6: Atypical mycobacteria, salmonella, histoplasma capsulatum, herpes zoster, HHV6, CMV, EBV, adenovirus, parvovirus.
7: Total IFN γ , CXCL9 and other inflammatory biomarkers in serum (e.g. IL-6, TNF α , sCD163 and sIL2R α)
8: this sample is collected for emapalumab treated patients only
9: Relevant procedures /medications are defined as any HSCT, blood product transfusion, stem cell boost, DLI or hematopoietic agents received since the previous visit/call.

Table 7b: Schedule of assessments – Follow-up period, withdrawal visit, unscheduled visit (Cohort 1, 2 and 3) - Patient weight < 30 kg

PERIOD (Duration)		FOLLOW UP (3 years)										Unscheduled Visit ⁴	
		FU 1 ¹	FU 2 ¹	FU 3 ¹	FU 4 ¹	FU 5 ¹	FU6 ¹ or EoS visit ^{1,2} or Withdrawal ³	Phone calls					
Days ± window		Week 1 ±2 days	Week 2 ±2 days	Week 4 ±2 days	Week 8 ±1 week	Week 12 ±1 week	Week 24 ±2 Weeks	6 months ±2 weeks from HSCT ²	1 year ±4 week from HSCT ^{1,2}	2 year ±4 weeks from HSCT ^{1,2}	3 year ±4 Weeks from HSCT ^{1,2}		
Clinical Assessments	Vital Signs (BP, HR, body temperature)	X	X	X	X	X	X					X	
	12-lead ECG											(X)	
	Chest X-ray	Only in case of clinical suspicion of pulmonary infection					X						(X)
	Physical Examination	As medically required					X						X
	Weight	X	X	X	X	X	X						X
	Record engraftment syndrome			X	X	X	X						(X)
Laboratory Procedures	Record GvHD, GF, graft rejection	X	X	X	X	X	X					(X)	
	Biochemistry and hematology including differential haematology ⁵	X		X	X	X	X					(X)	
	Re-occurrence or progression of underlying malignant disease (MRD)			X*	X*	X*	X					(X)	
	Urinalysis	X	X	X	X	X	X					(X)	
	Search for infections ⁶	If an infection is suspected										(X)	
	TB testing						X						(X)
	Donor chimerism						X*						(X)
	Inflammatory biomarkers ⁷	X	X	X	X	X	X						(X)
	HLA antibodies against donor cells						X*						(X)
	PK			X	X	X	X ⁸						(X)
Antibodies against emapalumab			X		X	X ⁸						(X)	
Survival check and GvHD occurrence recording								X				(X)	
Relevant concomitant medications/procedures⁹		X						X				X	
AEs		X						Only SAEs related to emapalumab				X	

Table 7b: Foot Notes
Abbreviations: FU: Follow Up; EoS: End of Study visit; BP: Blood Pressure; HR: Heart Rate; ECG: Electrocardiogram; MRD: Minimal Residual Disease; HZ: Herpes zoster; GF: Graft Failure; GvHD: Graft versus Host Disease; HLA: Human Leukocyte Antigen; PK: pharmacokinetics; AEs: Adverse Events
*This sample is not collected for patients < 15 kg and will be performed as clinically indicated
1: This visit is foreseen for emapalumab treated patients. FU week 1 to be scheduled 1 week \pm 2 days from last study drug administration or 1 week after EoT (in case of treatment discontinuation or engraftment before the last dosing 15).
2: This visit is foreseen for non-emapalumab treated patients. The EoS visit for non-emapalumab treated patients must be scheduled within 1 week from the last day in the monitoring periods.
3: In case of premature withdrawal from the study for any reason (except informed consent withdrawal), patients should undergo a withdrawal visit within 1 week from the date of withdrawal.
4: Assessments marked as (X) will be done if considered medically relevant
5: Biochemistry: Glucose, C-reactive protein (CRP), Sodium, Potassium, Chloride, Calcium, Magnesium and Phosphate, AST, ALT, γ GT, ALP, LDH, bilirubin (total, direct and indirect), triglycerides, cholesterol (total and HDL), Albumin, creatinine, urea (fasting conditions whenever possible), Ferritin. Hematology: hematocrit, hemoglobin, platelets, RBC, WBC. Hematology differential: lymphocytes, monocytes, neutrophils.
6: Atypical mycobacteria, salmonella, histoplasma capsulatum, herpes zoster, HHV6, CMV, EBV, adenovirus, parvovirus.
7: Total IFNg, CXCL9 and other inflammatory biomarkers in serum (e.g. IL-6, TNF α , sCD163 and sIL2R α)
8: This sample is collected for emapalumab treated patients only
9: Relevant procedures /medications are defined as any HSCT, blood product transfusion, stem cell boost, DLI or hematopoietic agents received since the previous visit/call

